7 DISCONTINUATION OF STUDY INTERVENTION AND PARTICIPANT WITHDRAWAL

7.1 Discontinuation of Study Intervention

Discontinuation of study intervention does not represent withdrawal from the study.

As certain data on clinical events beyond study intervention discontinuation may be important to the study, they must be collected through the participant's last scheduled follow-up, even if the participant has discontinued study intervention. Therefore, all participants who discontinue study intervention prior to completion of the protocol-specified treatment period will still continue to be monitored in this study and participate in the study visits and procedures as specified in Section 1.3 and Section 8.10.3 unless the participant has withdrawn from the study.

Participants may discontinue study intervention at any time for any reason or be dropped from the study intervention at the discretion of the investigator should any untoward effect occur. In addition, a participant may be discontinued from study intervention by the investigator or the Sponsor if study intervention is inappropriate, the study plan is violated, or for administrative and/or other safety reasons. Specific details regarding procedures to be performed at study intervention discontinuation are provided in Section 8.1.11.

A participant must be discontinued from study intervention but continue to be monitored in the study for any of the following reasons:

- The participant or participant's legally acceptable representative requests to discontinue study intervention
- The participant interrupts study intervention administration for more than 12 consecutive weeks.
- The participant has a medical condition or personal circumstance that, in the opinion of the investigator and/or Sponsor, placed the participant at unnecessary risk from continued administration of study intervention.
- The participant has a confirmed positive serum pregnancy test.
- Unacceptable adverse experiences as described in Section 8.3.
- Use of prohibited concomitant medications as described in Section 6.5.2.
- Intercurrent illness other than another malignancy as noted above that prevents further administration of treatment.
- Investigator's decision to discontinue treatment.
- Side effects and/or concomitant medications required for treatment of HIV and/or its complications that are incompatible with continued study treatment (exceptions are permissible but should be discussed with the Sponsor).
- Confirmed radiographic disease progression outlined in Section 8.2 (exception if the Sponsor approves treatment continuation following confirmed PD per iRECIST)

- Any progression or recurrence of any malignancy, or any occurrence of another malignancy that requires active treatment
- Any study intervention-related toxicity specified as a reason for permanent discontinuation as defined in the guidelines for dose modification due to AEs in Section 6.6.
- Discontinuation of treatment may be considered for participants who have attained a confirmed complete response (CR) and have been treated for at least 8 cycles (at least 24 weeks), receiving at least 2 doses of pembrolizumab alone (Arm 3) or 2 cycles of the combination therapy (Arms 1 and 2) including 2 doses of pembrolizumab and at least 80% of the planned doses of V937 beyond the date when the initial CR was declared.
- Completion of 35 treatments (approximately 2 years) with pembrolizumab

For participants who are discontinued from study intervention but continue to be monitored in the study, all visits and procedures, as outlined in the SoA, should be completed.

Discontinuation from study intervention is “permanent.” Once a participant is discontinued, he/she shall not be allowed to restart study intervention.

7.2 Participant Withdrawal From the Study

A participant must be withdrawn from the study if the participant or participant’s legally acceptable representative withdraws consent from the study.

If a participant withdraws from the study, they will no longer receive study intervention or be followed at scheduled protocol visits.

Specific details regarding procedures to be performed at the time of withdrawal from the study, as well as specific details regarding withdrawal from future biomedical research, are outlined in Section 8.1.11. The procedures to be performed should a participant repeatedly fail to return for scheduled visits and/or if the study site is unable to contact the participant are outlined in Section 7.3.

7.3 Lost to Follow-up

If a participant fails to return to the clinic for a required study visit and/or if the site is unable to contact the participant, the following procedures are to be performed:

- The site must attempt to contact the participant and reschedule the missed visit. If the participant is contacted, the participant should be counseled on the importance of maintaining the protocol-specified visit schedule.
- The investigator or designee must make every effort to regain contact with the participant at each missed visit (eg, telephone calls and/or a certified letter to the participant’s last

known mailing address or locally equivalent methods). These contact attempts should be documented in the participant's medical record.

- Note: A participant is not considered lost to follow-up until the last scheduled visit for the individual participant. The missing data for the participant will be managed via the prespecified statistical data handling and analysis guidelines.

8 STUDY ASSESSMENTS AND PROCEDURES

- Study procedures and their timing are summarized in the SoA.
- Adherence to the study design requirements, including those specified in the SoA, is essential and required for study conduct.
- The investigator is responsible for ensuring that procedures are conducted by appropriately qualified (by education, training, and experience) staff. Delegation of study site personnel responsibilities will be documented in the Investigator Trial File Binder (or equivalent).
- All study-related medical decisions must be made by an investigator who is a qualified physician.
- All screening evaluations must be completed and reviewed to confirm that potential participants meet all eligibility criteria. The investigator will maintain a screening log to record details of all participants screened and to confirm eligibility or record reasons for screening failure, as applicable.
- Procedures conducted as part of the participant's routine clinical management (eg, blood count) and obtained before signing of ICF may be utilized for screening or baseline purposes provided the procedure met the protocol-specified criteria and were performed within the time frame defined in the SoA.
- Additional evaluations/testing may be deemed necessary by the investigator and or the Sponsor for reasons related to participant safety. In some cases, such evaluation/testing may be potentially sensitive in nature (eg, HIV, Hepatitis C), and thus local regulations may require that additional informed consent be obtained from the participant. In these cases, such evaluations/testing will be performed in accordance with those regulations.

The approximate amount of blood collected from each participant over the duration of the study is provided in the Procedures Manual.

Repeat or unscheduled samples may be taken for safety reasons or for technical issues with the samples.

8.1 Administrative and General Procedures

8.1.1 Informed Consent

The investigator or medically qualified designee (consistent with local requirements) must obtain documented informed consent from each potential participant or their legally acceptable representative prior to participating in this clinical study or future biomedical research. If there are changes to the participant's status during the study (eg, health or age of majority requirements), the investigator or medically qualified designee must ensure the appropriate documented informed consent is in place.

8.1.1.1 General Informed Consent

Informed consent given by the participant or their legally acceptable representative must be documented on a consent form. The form must include the trial protocol number, trial protocol title, dated signature, and agreement of the participant (or his/her legally acceptable representative) and of the person conducting the consent discussion.

A copy of the signed and dated informed consent form should be given to the participant (or their legally acceptable representative) before participation in the study.

The initial ICF, any subsequent revised ICF, and any written information provided to the participant must receive the IRB/IEC's approval/favorable opinion in advance of use. The participant or his/her legally acceptable representative should be informed in a timely manner if new information becomes available that may be relevant to the participant's willingness to continue participation in the study. The communication of this information will be provided and documented via a revised consent form or addendum to the original consent form that captures the participant's or the participant's legally acceptable representative's dated signature.

If the investigator recommends continuation of study intervention beyond disease progression, the participant or their legally acceptable representative will be asked to provide documented informed consent.

Specifics about the study and the study population are to be included in the study informed consent form template at the protocol level.

Informed consent will adhere to IRB/IEC requirements, applicable laws and regulations, and Sponsor requirements.

8.1.1.2 Consent and Collection of Specimens for Future Biomedical Research

The investigator or medically qualified designee will explain the future biomedical research consent to the participant, or the participant's legally acceptable representative, answer all of his/her questions, and obtain documented informed consent before performing any procedure related to future biomedical research. A copy of the informed consent will be given to the participant before performing any procedure related to FBR.

8.1.2 Inclusion/Exclusion Criteria

All inclusion and exclusion criteria (Sections 5.1 and 5.2) will be reviewed by the investigator, who is a qualified physician, to ensure that the participant qualifies for the study.

8.1.3 Participant Identification Card

All participants will be given a participant identification card identifying them as participants in a research study. The card will contain study site contact information (including direct telephone numbers) to be used in the event of an emergency. The investigator or qualified designee will provide the participant with a participant identification card immediately after the participant provides documented informed consent. At the time of intervention randomization, site personnel will add the treatment/randomization number to the participant identification card.

The participant identification card also contains contact information for the emergency unblinding call center so that a healthcare provider can obtain information about study intervention in emergency situations where the investigator is not available.

8.1.4 Medical History

A medical history will be obtained by the investigator or qualified designee. The medical history will collect all active conditions and any condition diagnosed within the prior 10 years that the investigator considers to be clinically significant. Details regarding the disease for which the participant has enrolled in this study will be recorded separately and not listed as medical history.

8.1.5 Disease Details

The investigator or qualified designee will obtain prior and current details regarding disease status.

8.1.6 Prior Oncology Treatment History

The investigator or qualified designee will record all prior cancer treatments including systemic treatments, radiation, and surgeries.

8.1.7 Prior and Concomitant Medications Review

8.1.7.1 Prior Medications

The investigator or qualified designee will review prior medication use, including any protocol-specified washout requirement, and record prior medication taken by the participant within 28 days before first dose of study intervention. Treatment for the disease for which the participant has enrolled in this study will be recorded separately and not listed as a prior medication.

8.1.7.2 Concomitant Medications

All treatments that the investigator considers necessary for a participant's welfare may be administered at the discretion of the investigator in keeping with the community standards of medical care, with the exceptions of those specifically excluded (see Section 6.5.2). All concomitant medication will be recorded on the eCRFs, including all prescription, OTC products, herbal supplements, and IV medications, and fluids. If changes occur during the study period, documentation of drug dosage, frequency, route, and date should also be included on the eCRF.

All concomitant medications received within 28 days prior to the first dose of study intervention and up to 30 days after the last dose of study intervention should be recorded. Concomitant medications administered 30 days after the last dose of study treatment should be recorded for SAEs and events of clinical interest (ECIs) as defined in Section 8.4.7.

The investigator or qualified designee will record medication, if any, taken by the participant during the study through the Safety Follow-up visit.

All medications related to reportable SAEs and ECIs should be recorded as defined in Section 8.4.7.

All new anticancer therapy initiated after the study start must be recorded in the eCRF. If a participant initiates another anticancer therapy other than the assigned study intervention(s), the study intervention(s) should be discontinued and the participant will move into the survival follow-up phase; if a participant initiates a new anticancer therapy within 30 days after the last dose of the study intervention, the 30-day Safety Follow-up Visit should occur before the first dose of the new therapy.

8.1.8 Assignment of Screening Number

All consented participants will be given a unique screening number that will be used to identify the participant for all procedures that occur prior to randomization. Each participant will be assigned only 1 screening number. Screening numbers must not be re-used for different participants.

Any participant who is screened multiple times will retain the original screening number assigned at the initial screening visit. Participants may be screened up to 2 times. Specific details on the screening/rescreening visit requirements are provided in Section 8.10.1.

8.1.9 Assignment of Treatment/Randomization Number

All eligible participants will be randomly allocated and will receive a treatment/randomization number. The treatment/randomization number identifies the participant for all procedures occurring after treatment randomization. Once a treatment/randomization number is assigned to a participant, it can never be re-assigned to another participant.

A single participant cannot be assigned more than 1 treatment/randomization number.

8.1.10 Study Intervention Administration

Administration of study medication will be monitored by the investigator and/or study staff.

Study intervention(s) will be administered by the investigator and/or study staff according to the specifications within the pharmacy manual.

Study intervention should begin within 3 days of randomization (for Arms 1 and 2) or C1D8 \pm 1 day (for Arm 3).

8.1.10.1 Timing of Dose Administration

In all arms of the study, pembrolizumab will be administered on Day 8 of Cycle 1 (28-day cycle) and on Day 1 of all subsequent cycles. V937 will be administered either IV (Arm 1) or ITu (Arm 2) on Days 1, 3, 5, and 8 of Cycle 1 (28 days); on Day 8 of Cycle 1, V937 will be administered 0.5 to 4 hours after a 200-mg dose of pembrolizumab infused over 30 minutes. For Cycles 2-8, V937 will be administered IV (Arm 1) or ITu (Arm 2) on Day 1 of each 21-day cycle, 0.5 to 4 hours after a 200-mg dose of pembrolizumab infused over 30 minutes. Each participant may undergo up to 11 administrations of V937 and may continue treatment with pembrolizumab for up to a total of 35 cycles (approximately 2 years).

In Cycle 1, for the first 4 doses of V937 in Arms 1 and 2, a window of 24 hours for dosing will be allowed to accommodate weekends. In Cycle 2, study intervention may be administered up to 3 days after the scheduled Day 1. Beginning in Cycle 3, study intervention may be administered up to 3 days before or after the scheduled Day 1.

Dosing interruptions are permitted in the case of medical/surgical events or logistical reasons that are not related to study therapy (eg, elective surgery, unrelated medical events, participant vacation, and/or holidays). Participants should be placed back on study therapy within 3 weeks of the scheduled interruption, unless otherwise discussed with the Sponsor Medical Monitor or designee. The reason for interruption should be documented in the participant's study record.

8.1.11 Discontinuation and Withdrawal

Participants who discontinue study intervention prior to completion of the treatment period should be encouraged to continue to be followed for all remaining study visits as outlined in the SoA and Section 8.10.3.

When a participant withdraws from participation in the study, all applicable activities scheduled for the End-of-Treatment Visit should be performed (at the time of withdrawal). Any AEs that are present at the time of withdrawal should be followed in accordance with the safety requirements outlined in Section 8.4 and Section 8.10.3.

8.1.11.1 Withdrawal From Future Biomedical Research

Participants may withdraw their consent for future biomedical research. Participants may withdraw consent at any time by contacting the investigator for the main study. If medical records for the main study are still available, the investigator will contact the Sponsor using the designated mailbox ([contact]). Subsequently, the participant's consent for future biomedical research will be withdrawn. A letter will be sent from the Sponsor to the investigator confirming the withdrawal. It is the responsibility of the investigator to inform the participant of completion of withdrawal. Any analyses in progress at the time of request for withdrawal or already performed prior to the request being received by the Sponsor will continue to be used as part of the overall research study data and results. No new analyses would be generated after the request is received.

In the event that the medical records for the main study are no longer available (eg, if the investigator is no longer required by regulatory authorities to retain the main study records) or the specimens have been completely anonymized, there will no longer be a link between the participant's personal information and their specimens. In this situation, the request for specimen withdrawal cannot be processed.

8.1.12 Participant Blinding/Unblinding

This is an open-label study; there is no blinding for this study.

8.1.13 Calibration of Equipment

The investigator or qualified designee has the responsibility to ensure that any device or instrument used for a clinical evaluation/test during a clinical study that provides information about inclusion/exclusion criteria and/or safety or efficacy parameters shall be suitably calibrated and/or maintained to ensure that the data obtained are reliable and/or reproducible. Documentation of equipment calibration must be retained as source documentation at the study site.

8.2 Efficacy/Immunogenicity Assessments

8.2.1 Tumor Imaging and Assessment of Disease

In addition to survival, efficacy will be assessed based on imaging evaluation of changes in tumor burden over time, until the participant is discontinued from the study or goes into survival follow-up. The process for image collection and transmission to the iCRO for BICR can be found in the Site Imaging Manual. Tumor imaging is strongly preferred to be acquired by CT. For the abdomen and pelvis, contrast-enhanced MRI may be used when CT with iodinated contrast is contraindicated, or when mandated by local practice. The same imaging technique should be used in a participant throughout the study to optimize the reproducibility of the assessment of existing and new tumor burden and improve the accuracy of the response assessment based on imaging. Note: for the purposes of assessing tumor imaging, the term "investigator" refers to the local investigator at the site and/or the radiological reviewer at the site or at an offsite facility. Tumor imaging schedule is based on calendar

days from the first administration of study intervention and will not be postponed due to delays in treatment cycles. Additional tumor imaging and medical photography may be performed as clinically indicated. Brain imaging is required for all participants with previously treated brain metastases at screening. Magnetic resonance imaging is preferred; however, CT imaging will be acceptable, if MRI is medically contraindicated.

Bone scans are also required for participants with a history of bone metastases and/or for those participants with new bone pain. Any supplemental imaging done to support a positive or negative bone scan, such as plain X-rays that may be acquired for correlation, should be submitted to the iCRO.

Other imaging modalities that may be collected, submitted to the iCRO, and included in response assessment include medical photography.

All scheduled imaging for all study participants will be submitted to the iCRO. In addition, imaging that is obtained at an unscheduled time point, for any reason (including suspicion of progression or other clinical reason), should also be submitted to the iCRO if it shows progression, or if it is used to support a response assessment. All imaging acquired within the protocol-specified window of time around a scheduled imaging visit can be classified as pertaining to that visit.

RECIST 1.1 and iRECIST assessment will be done for both injected and noninjected lesions. Injecting a lesion after treatment has begun will not render it “nonevaluable” for response assessment purposes.

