8.2.1.2 Tumor Imaging During the Study

The first on-study imaging assessment should be performed at 9 weeks (63 days \pm 7 days) from the date of the first dose of pembrolizumab. Subsequent tumor imaging should be performed every 9 weeks (63 days \pm 7 days) or more frequently if clinically indicated. After 54 weeks (379 days \pm 7 days), participants who remain on treatment will have imaging performed every 12 weeks (84 days \pm 7 days). Imaging timing should follow calendar days and should not be adjusted for delays in cycle starts. Imaging should continue to be performed until disease progression is identified by the investigator (unless the investigator elects to continue treatment and follow iRECIST), the start of new anticancer treatment, withdrawal of consent, or death, whichever occurs first. All supplemental imaging must be submitted to the iCRO.

Objective response should be confirmed by a repeat imaging assessment. Tumor imaging to confirm PR or CR should be performed at least 4 weeks after the first indication of a response is observed. Participants will then return to regular scheduled imaging, starting with the next scheduled imaging time point. Participants who receive additional imaging for confirmation do not need to undergo the next scheduled tumor imaging if it is less than 4 weeks later; tumor imaging may resume at the subsequent scheduled imaging time point. Note: Response does not typically need to be verified in real time by the BICR.

Per iRECIST (Section 8.2.1.5), disease progression should be confirmed by the site 4 to 8 weeks after site-assessed first radiologic evidence of PD in clinically stable participants. Participants who have unconfirmed disease progression may continue on treatment at the discretion of the investigator until progression is confirmed by the site provided they have met the conditions detailed in Section 8.2.1.5. Participants who receive confirmatory imaging do not need to undergo the next scheduled tumor imaging if it is less than 4 weeks later; tumor imaging may resume at the subsequent scheduled imaging time point, if clinically stable. Participants who have confirmed disease progression by iRECIST, as assessed by the site, will discontinue study intervention. Exceptions are detailed in Section 8.2.1.5.

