8.2.1.3 End-of-Treatment and Follow-up Tumor Imaging

For participants who discontinue study intervention, tumor imaging should be performed at the time of treatment discontinuation (± 4 week window). If previous imaging was obtained within 4 weeks prior to the date of discontinuation, then imaging at treatment discontinuation is not mandatory. For participants who discontinue study intervention due to documented disease progression, this is the final required tumor imaging if the investigator elects not to implement iRECIST.

For participants who discontinue study intervention without documented disease progression, every effort should be made to continue monitoring disease status by tumor imaging using the same imaging schedule used while on treatment calculated from the date of first pembrolizumab administration (see Section 8.2.1.2) until the start of a new anticancer treatment, disease progression, pregnancy, death, withdrawal of consent, or the end of the study, whichever occurs first.

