8.10.2 Treatment Period/Vaccination Visit

The treatment period in each treatment arm begins with Cycle 1 (Arms 1 and 2: Cycle 1 Day 1 and Arm 3: Cycle 1 Day 8;) and may continue for up to 35 cycles (approximately 2 years) from the start of treatment until disease progression, unacceptable AE(s), intercurrent illness that prevents further administration of treatment, investigator's decision to withdraw the participant, participant withdraws consent, pregnancy of the participant, noncompliance with study treatment or procedure requirements, or administrative reasons requiring cessation of treatment. Each cycle includes study drug administration and all associated assessments as outlined in the SoA (Section 1.3).

Visit requirements are outlined in the SoA (Section 1.3). Specific procedure-related details are provided in Section 8.1.

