8.10.4.2 Follow-up Visits

Participants who complete the protocol-required cycles of study intervention or who discontinue study intervention for a reason other than disease progression will begin the Imaging Follow-up and should be assessed every 9 weeks to monitor disease status. Every effort should be made to collect information regarding disease status until the start of new anticancer therapy, disease progression, death, or the end of study, whichever occurs first. Information regarding poststudy anticancer treatment will be collected if new treatment is initiated. Participants who completed all imaging assessments and/or will not have further efficacy assessments must enter the Survival Follow-up Phase.

Due to early study discontinuation, participants may be enrolled in a pembrolizumab extension study, if available, to continue pembrolizumab monotherapy. The Imaging Follow-up will not be required for such participants.

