9.4 Analysis Endpoints

9.4.1 Efficacy/Pharmacokinetics/Pharmacodynamic Endpoints

Primary Endpoint

- Objective Response (OR): a confirmed complete response (CR) or partial response (PR) per RECIST 1.1 based on BICR. ORR is the proportion of participants with objective response.

Secondary Endpoints

- PFS: time from randomization to the first documented PD per RECIST 1.1 based on BICR or death from any cause, whichever occurs first. See Section 9.6.1 for the definition of censoring.
- DOR: time from the first documented evidence of CR or PR until PD per RECIST 1.1 as assessed by BICR or death due to any cause, whichever occurs first, in participants demonstrating CR or PR.
- OS: time from randomization to the date of death due to any cause.

CCI

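### Section 8.2.1 starts the imaging calendar at a different point from Sections 8.2.1.2 and 8.2.1.3; a site that follows it scans Arms 1 and 2 nominally 7 days before Arm 3, which can bias the PFS hazard ratio only against V937

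*Combined protocol and SAP*

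**What the plan says.** **Start of the imaging calendar.**
- Section 8.2.1 (general imaging rules) counts calendar "days from the first administration of study intervention and will not be postponed due to delays in treatment cycles".
- Section 8.2.1.2 places the first on-study scan at 9 weeks "from the date of the first dose of pembrolizumab".
- Section 8.2.1.3 continues imaging after treatment stops on a schedule "calculated from the date of first pembrolizumab administration".

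**Where those dates fall.** Section 8.10.2 gives the start of treatment as "Arms 1 and 2: Cycle 1 Day 1 and Arm 3: Cycle 1 Day 8", and Section 8.1.10 agrees. For pembrolizumab, Section 8.1.10.1 says: "In all arms of the study, pembrolizumab will be administered on Day 8 of Cycle 1".

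**How PFS uses the scans.** Section 9.4.1 defines "PFS: time from randomization to the first documented PD per RECIST 1.1 based on BICR or death from any cause". Section 9.6.1.2 dates progression at the first assessment that documents it and censors participants without an event at their last disease assessment. It then applies a stratified log-rank test and a stratified Cox model. The only PFS sensitivity analysis named there uses the investigator's reading.

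**Imaging after treatment stops.** Section 8.10.4.2 says that participants "should be assessed every 9 weeks to monitor disease status". Section 8.2.1.3 asks for the "same imaging schedule used while on treatment calculated from the date of first pembrolizumab administration", and Section 8.2.1.2 widens that schedule from 9 to 12 weeks after week 54.

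**The concern.** In Arm 3 the first study intervention is the first pembrolizumab dose, so both rules give the same date. In Arms 1 and 2 they give dates 7 days apart. The text available does not say which rule governs.

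A radiographic progression enters the PFS analysis on its scan date. If one arm's scans come a week earlier, its progressions are dated earlier. On those days the other arm's progressions, already present but not yet imaged, still count as progression-free. The log-rank test and Cox model read this as a treatment difference. Arm 3's dates are the same under both rules, so use of the 8.2.1 rule can only move the V937 arms earlier, and the error has one direction. An investigator-read PFS analysis uses the same scan dates and would not reveal it.

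The off-treatment conflict is a separate matter. It concerns which assessments count as missed under the DOR censoring rules in Table 13.

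**Working it through.** **1. Dates, counted from C1D1 with C1D8 falling 7 days later.** The scan interval is 9 × 7 = 63 days.

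| Rule | First scan, Arms 1 and 2 | First scan, Arm 3 | Gap |
|---|---|---|---|
| 8.2.1 (first study intervention) | 0 + 63 = day 63, window 56–70 | 7 + 63 = day 70, window 63–77 | 7 days |
| 8.2.1.2 and 8.2.1.3 (first pembrolizumab) | 7 + 63 = day 70, window 63–77 | day 70, window 63–77 | 0 |

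The gap carries to every later scheduled scan. The 1-day window on C1D8 makes it 6 to 8 days in practice. A day-58 scan in Arm 1 or 2 is on time under one rule and 5 days early under the other.

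**2. Effect on the HR.** The readable text gives no median PFS, PFS event count or target HR, so there is no stated figure to reproduce. The effect was simulated.
- *From the documents:* scans every 63 days to week 54 (54 × 7 = 378 days; Section 8.2.1.2 prints 379), then every 84; a 7-day window either way; randomization 0 to 3 days before C1D1; progression dated at the scan; censoring at the last scan; Cox model with Efron ties.
- *Assumed:* exponential PFS with medians of 3 to 18 months; 10% of PFS events are deaths, dated exactly; follow-up spread over 12 to 30 months; no stratification.

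Apparent HR (V937 combination versus pembrolizumab) when the true HR is 1, with 200,000 per arm:

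| Median PFS (months) | 8.2.1 rule, scans on nominal day | 8.2.1 rule, scans uniform over ±7 days | Common clock (nominal day / ±7 days) |
|---|---|---|---|
| 3 | 1.198 | 1.130 | 1.000 / 1.004 |
| 6 | 1.115 | 1.074 | 1.002 / 0.995 |
| 9 | 1.091 | 1.062 | 0.995 / 1.003 |
| 12 | 1.090 | 1.055 | 0.998 / 1.000 |
| 18 | 1.076 | 1.043 | 0.998 / 0.998 |

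A true HR of 0.70 would appear as 0.73 to 0.77 (control medians of 6 and 12 months).

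**3. Partial use of the 8.2.1 rule.** With scans spread over the window and medians of 3 to 12 months, the apparent HR is about 1.03 to 1.06 if half of Arm 1 and 2 participants are scanned by that rule. It is about 1.01 to 1.03 if a quarter are.

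**4. Against sampling error.** At 135/3 = 45 per arm, the simulated SE of the log HR is 0.228 (median 6 months) and 0.262 (median 12 months). Even if all 90 participants in a comparison had an event, the SE would be about √(1/45 + 1/45) = 0.211. The largest bias is ln 1.198 = 0.181, and at a 6-month median on nominal days it is ln 1.115 = 0.109. Both are below one SE. In 4,000 replicates at medians of 6 and 12 months, full use of the 8.2.1 rule gave false findings against V937 (two-sided 5% test) in 3.2% to 6.3% of trials, compared with about 2.5% under a common clock. False findings in its favor fell to about 1%.

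**5. Off-treatment interval and DOR.** Take a responder off treatment, scanned at week 54, with no scan until progression is found at week 78.
- *12-weekly schedule:* the week 66 scan is missed and week 78 is on schedule. With one missed assessment, Table 13 counts an event.
- *9-weekly schedule:* the week 63 and week 72 scans are missed. With two consecutive missed assessments, Table 13 censors at week 54.

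The same data give opposite outcomes.

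**The case against.** The strongest reply is that Section 8.2.1 alone cannot schedule a scan, because it gives no interval. The interval is in Section 8.2.1.2, which carries its own anchor, and Section 8.2.1.3 repeats that anchor. Both give every arm the same clock, and the sentence in 8.2.1 can be read as mainly saying that scans are not delayed when cycles are. The imaging rows of Tables 2 to 4 and the Imaging Manual, neither of which is available here, may also settle the matter. This stands: the wording conflict is certain, but actual use of the 8.2.1 rule is not known.

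It is also fair that PFS is secondary, that the stated hypothesis concerns ORR only, that Table 14 lists PFS for estimation, and that early closure leaves few scans to reschedule. The off-treatment conflict is the same for all arms by design and matters only after week 54. Section 8.10.4.2 waives imaging follow-up for participants who enter the extension study.

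A reader might infer more than the documents support:
- *That the PFS HR is biased.* It is biased only to the extent that sites use the 8.2.1 rule.
- *That the V937 arms would always be scanned earlier.* The gap is nominal, and the two windows overlap from day 63 to day 70.
- *That timing PFS from randomization is a further fault.* Randomization is at most 3 days before C1D1, and this origin creates no arm difference when scans share one anchor.
- *That OS is affected.* OS does not depend on scan dates.

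**Conclusion.** The contradiction is real and is in the current text. Its effect on PFS is conditional. If every site used the 8.2.1 rule, the apparent HR under no true effect would be about 1.04 to 1.20 across assumed medians of 3 to 18 months. The upper end needs a 3-month median and scans on the nominal day. Under Sections 8.2.1.2 and 8.2.1.3 it would be about 1.00. The direction can only be against V937.

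The bias is below sampling error at 45 per arm in every case examined, and a smaller final enrollment would widen that sampling error. OS and the comparison of Arm 1 with Arm 2 are unaffected, and confirmed ORR should be little affected. The off-treatment conflict is also real; its stake is DOR censoring after week 54, and no overall effect was computed.

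Severity is minor to moderate. The size rests on the assumed medians, the 10% share of deaths and the assumed follow-up; the direction follows from the documents.

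**What to change.** 1. Align Section 8.2.1 with the anchor that Sections 8.2.1.2 and 8.2.1.3 already share, which falls on the same day in all arms. Moving every scan to a new anchor, such as randomization or C1D1, is more than is needed.
2. Reconcile the post-week-54 off-treatment interval in Section 8.10.4.2 with Section 8.2.1.3, so that a missed assessment in Table 13 has one meaning.
3. For scans already done, add a PFS sensitivity analysis that dates BICR progression to the nominal scan visit or uses an interval-censored model. A listing by arm of which clock was used would show whether the conflict had any effect.

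The cost is protocol wording and one extra analysis of existing data. No extra scans are needed.
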